9.5 Determination of Sample Size

The primary endpoint is PFS. It is expected that the experimental regimen will achieve better efficacy compared to the standard of care for this population. We will enroll a total of 60 patients with an accrual rate of 4 patients per month. All patients will be followed for at least 3 years or until death. The final analysis will be performed when the last patient is followed for 3 years. When the sample size is 60, a two-sided 95% CI for the PFS rate at 2 years will extend 0.106 from the observed rate for an expected rate of 77% (nQuery Advisor 7.0).

Proprietary Information of MD Anderson

9.6 Trial Monitoring

Due to the fast accrual planned for the study and long median PFS time expected for the experimental regimen, a formal futility monitoring rule is not feasible.

Because of the limited number of patients who have received the combination treatment, for patient safety we will monitor the prohibitive toxicity, defined as any treatment-related death or frequent discontinuation of treatment during cycles 1 and 2. The prohibitive toxicity rate of 15% or higher will be considered unacceptable. The prior probability of the rate is assumed to follow a Beta (0.3, 1.7) distribution with two patients worth of information. We will monitor patients by a cohort size of 10. At any time after at least 10 patients have completed toxicity evaluations, the trial will be stopped if the following statement is true

$$\Pr[\text{prohibitive toxicity rate} > 15\% \mid \text{data}] > 0.95,$$

which means that the trial will be stopped for toxicity if the posterior probability of the rate being greater than 15% is greater than 95%.

Patients will be monitored by a cohort size of 10 according to the following stopping boundaries for prohibitive toxicity at cycles 1 and 2.

Number of patients evaluated	Stop if \geq prohibitive toxicities observed
10	4-10
20	7-20
30	9-30
40	11-40
50	13-50
60	Always stop with this many patients

Operating characteristics for the stopping rules

For prohibitive toxicity monitoring

True Prohibitive Toxicity Rate	Probability Stop Early	Average sample size
0.05	0.0011	59.95
0.10	0.0157	59.23
0.15	0.0902	56.46

Proprietary Information of MD Anderson

0.20	0.2956	49.65
0.25	0.5924	39.48
0.30	0.8337	29.33

The above stopping boundaries and operating characteristics are calculated using MultLean (v.2.1.0) design software downloaded from <http://biostatistics.mdanderson.org/SoftwareDownload>.

Any treatment-related death occurring beyond cycle 2 will result in pause in accrual pending complete evaluation and discussion between the Principal Investigator and the FDA.

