5.3 Treatment Schedule

Patients will receive 12 cycles of lenalidomide, 15mg daily on days 1-21 of cycle 1, and 20mg daily on days 1-21 (± 2 days) of cycles 2 through 12. Cycles will be 28 days in length. Patients will receive rituximab, 375mg/m² on days 1, 8 (± 2 days), 15 (± 2 days), and 22 (± 2 days) of cycle 1, and day 1 (± 2 days) of cycles 2 through 12. Patients will receive ibrutinib 560mg daily, starting on day 1 of cycle 1 and continued through 12 cycles. Therapy is continued for 12 cycles or until disease progression, unacceptable toxicity, or voluntary withdrawal.

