9.1.2 Safety Monitoring

Proprietary Information of MD Anderson

The Principal Investigator or a physician designee will assess each subject to evaluate for potential new or worsening AEs as specified in the Trial Flow Chart, Appendix 13.1 and more frequently if clinically indicated. Adverse experiences will be graded and recorded throughout the study and during the follow-up period according to NCI CTCAE Version 4.03. Toxicities will be characterized in terms regarding seriousness, causality, toxicity grading, and action taken with regard to trial treatment. The study investigators and data coordinators are responsible for entering the data and safety for this study including causality. For both AEs and SAEs, the Investigator will provide a record of the start and stop dates of the event.

Safety data will be monitored by the Principal Investigator and in accordance with institutional policies. The Investigator will record the action taken with the study drugs as a result of an AE or SAE, as applicable (e.g., discontinuation, interruption, or reduction of study drugs, as appropriate) and report if concomitant and/or additional treatments were given for the event. AEs and SAEs will be reviewed on an ongoing basis to identify safety concerns.

For subjects with a history of Hepatitis B or C, standard of care monitoring for viral reactivation will be conducted. Subjects with a history of Hepatitis B will be required to undergo hepatitis B reactivation prophylaxis unless contraindicated.

All SAEs that have not resolved upon discontinuation of the subject's participation in the study must be followed until recovered, recovered with sequelae, not recovered or death (due to the SAE).

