Unanticipated Adverse Events for Drugs and Devices". Unless stated otherwise in the protocol, all SAEs, expected or unexpected, must be reported to the IND Office, regardless of attribution (within 5 working days of knowledge of the event).

- **All life-threatening or fatal events**, that are unexpected, and related to the study drug, must have a written report submitted within **24 hours** (next working day) of knowledge of the event to the Safety Project Manager in the IND Office.
- Unless otherwise noted, the electronic SAE application (eSAE) will be utilized for safety reporting to the IND Office and MDACC IRB.
- Serious adverse events will be captured from the time a signed and dated ICF is obtained until 30 days following the last dose of study drug, unless the participant withdraws consent. Serious adverse events must be followed until clinical recovery is complete and laboratory tests have returned to baseline, progression of the event has stabilized, or there has been acceptable resolution of the event.
- Additionally, any serious adverse events that occur after the 30 day time period that are related to the study treatment must be reported to the IND Office. This will include the development of a secondary malignancy, except superficial, non-melanoma skin cancers or carcinoma in situ.

Reporting to FDA:

- Serious adverse events will be forwarded to FDA by the IND Sponsor (Safety Project Manager IND Office) according to 21 CFR 312.32.

It is the responsibility of the PI and the research team to ensure serious adverse events are reported according to the Code of Federal Regulations, Good Clinical Practices, the protocol guidelines, the sponsor's guidelines, and Institutional Review Board policy. Safety data includes adverse events, product quality complaints (PQCs), and special situations including pregnancies.

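### Section 9.6 pauses accrual for a single treatment-related death only after cycle 2, and states no such pause for a death in cycles 1–2, the window it monitors for safety

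*Combined protocol and SAP*

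**What the plan says.** Section 9.6 gives its reason for toxicity monitoring: "Because of the limited number of patients who have received the combination treatment, for patient safety we will monitor the prohibitive toxicity". The monitored event is "defined as any treatment-related death or frequent discontinuation of treatment during cycles 1 and 2". A rate of 15% or higher is unacceptable, the prior is Beta(0.3, 1.7), and the trial stops if the posterior probability that the rate exceeds 15% is above 0.95. On timing: "At any time after at least 10 patients have completed toxicity evaluations, the trial will be stopped" if that condition is met. The resulting boundaries, for cycles 1 and 2, are 4/10, 7/20, 9/30, 11/40 and 13/50.

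The last sentence of section 9.6 adds a separate rule: "Any treatment-related death occurring beyond cycle 2 will result in pause in accrual pending complete evaluation" and discussion between the Principal Investigator and the FDA.

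Other provisions reach a death in any cycle. Sections 3.3 and 9.1.2 provide continuing review ("AEs and SAEs will be reviewed on an ongoing basis to identify safety concerns"). Section 10.1.2 requires SAE reports to the IND Office and IRB, and "Serious adverse events will be forwarded to FDA by the IND Sponsor". Section 8.3 lists termination of the study by the investigator. None of these states a consequence for accrual.

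**The concern.** A treatment-related death after cycle 2 pauses enrolment automatically. In cycles 1–2 the same event adds one to a pooled count designed to detect a composite rate above 15%, and that count cannot act on a single death or before 10 patients are evaluated. The text does not say whether the pause also applies to an early death.

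The plan singles out cycles 1–2 because few people have received the combination, yet for one isolated toxic death the automatic response there is weaker than later. Whether new patients keep entering after such a death is left to judgement, in a single-center study whose safety data are monitored by its own Principal Investigator.

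**Working it through.** **Inputs.** From section 9.6: Beta(0.3, 1.7) prior, 15% limit, 0.95 cut-off, cohorts of 10, and the boundaries. From section 9.5: "We will enroll a total of 60 patients with an accrual rate of 4 patients per month". From section 5.3: "Cycles will be 28 days in length". The documents give no early toxic-death rate, so the death and discontinuation rates below are assumptions.

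**1. Reproducing the plan's figures.** With x events in n patients the posterior is Beta(0.3 + x, 1.7 + n − x). The smallest x with Pr(rate > 0.15) > 0.95 is 4, 7, 9, 11 and 13 at n = 10, 20, 30, 40 and 50, which matches the table. Exact binomial recursion over these five looks gives stopping probabilities of 0.0011, 0.0157, 0.0902, 0.2956, 0.5924 and 0.8337 at true rates 0.05 to 0.30, again as tabulated.

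**2. What the boundary does with a few early deaths.** At n = 10:

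| Events in 10 | Posterior | Pr(rate > 15%) | Stop? |
|---|---|---|---|
| 1 | Beta(1.3, 10.7) | 0.26 | no |
| 2 | Beta(2.3, 9.7) | 0.59 | no |
| 3 | Beta(3.3, 8.7) | 0.84 | no |
| 4 | Beta(4.3, 7.7) | 0.954 | yes |

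If every event were a death, 3/10, 6/20, 8/30, 10/40 or 12/50 would not trigger the written rule.

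**3. Timing of the first look.** The tenth patient enrols at 10/4 = 2.5 months. Two cycles last 2 × 28 = 56 days, or 56/30.44 = 1.84 months. The first look therefore falls at about 4.34 months, when 4 × 4.34 ≈ 17 patients are enrolled. This assumes constant accrual; section 9.6 states no hold between cohorts.

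**4. How often the gap would matter.** With an assumed cycle 1–2 toxic-death rate q and no other counted event, the chance of at least one death in n patients is 1 − (1 − q)^n. The chance that the boundary fires comes from the recursion in step 1.

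| q | Expected deaths in 60 | At least 1 in first 10 | At least 1 in 60 | Boundary fires |
|---|---|---|---|---|
| 1% | 0.6 | 9.6% | 45% | 0.0002% |
| 2% | 1.2 | 18.3% | 70% | 0.003% |
| 5% | 3.0 | 40.1% | 95% | 0.11% |
| 10% | 6.0 | 65.1% | 99.8% | 1.6% |

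**5. With discontinuations counted.** The firing probability depends on the total event rate.

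- 2% deaths + 8% discontinuations = 10%: fires 1.6%; at least one death in 60, 70%.
- 5% + 5% = 10%: fires 1.6%; at least one death, 95%.
- 5% + 10% = 15%: fires 9.0%; at least one death, 95%.

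**6. Sensitivity to the look schedule.** The plan also says the rule may act at any time after 10 patients. Applying the posterior criterion after every patient from 10 to 59 raises the firing probability from 1.6% to 2.6% at a 10% event rate and from 9.0% to 15.1% at 15%. The posteriors in step 2 do not change, so one to three events in 10 still do not stop the trial.

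**The case against.** The strongest reply is that the two rules are complementary. Cycles 1–2 have a formal rule that can stop the trial. No boundary exists after cycle 2, and the pause fills that space. A stop and a pause differ in kind, so ranking one as weaker is partly a judgement. That is fair in general, but for a single death the comparison is direct: one rule acts and the other cannot.

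A second reply is that a rule aimed at a 15% composite rate is bound to fire rarely at 1–10%, as the plan's own table shows. This is true, and the boundary is not faulty. The point is that it is the only automatic consequence an early death has.

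Third, nothing in the documents suggests a high early toxic-death rate. Section 1 describes the phase 1 experience with the triplet (22 subjects) as tolerable, reports no dose-limiting toxicities, and reports no toxic deaths in the lenalidomide–rituximab phase 2 study. The 1% and 2% rows are therefore closer to that evidence than the 5% and 10% rows. However, the phase 1 data are preliminary and spread over several dose levels, and the phase 2 study did not include ibrutinib.

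Finally, review, SAE reporting and the investigator's power to terminate would make prolonged inaction after several deaths unlikely. They would do the same after cycle 2, where the plan still prescribes a pause.

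**Conclusion.** The concern holds and should be fixed. Section 9.6 attaches an automatic accrual pause to a treatment-related death only after cycle 2, and no section states an accrual consequence for one in cycles 1–2 beyond its count toward the boundaries. Up to three such deaths in the first 10 patients would leave the written rule untriggered, and about 17 patients would be enrolled before it could first be applied.

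The wording gap and the posterior values need no assumption about toxicity. How often the gap would matter does: at assumed early toxic-death rates of 1% to 2%, the chance of at least one such death in 60 patients is 45% to 70%, with almost no chance that deaths alone reach a boundary. The finding predicts no high death rate and does not touch the efficacy analysis or the reporting rules.

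**What to change.** State in section 9.6 what a treatment-related death does to accrual in every cycle. One way is to delete the words that confine the existing pause sentence to deaths after cycle 2, and to add: *Treatment-related deaths in cycles 1 and 2 also continue to count toward the stopping boundaries above.* If the difference is intended, say instead what happens to accrual after a death in cycles 1–2, and why.

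The prohibitive-toxicity definition, prior, boundaries, sample size and study procedures stay unchanged. The cost is possible pauses of unstated length. At assumed early toxic-death rates of 1%, 2%, 5% and 10%, the chance of at least one added pause is at most 45%, 70%, 95% and 99.8%. Deaths among the last 4 × 1.84 ≈ 7 patients may come after accrual has closed; counting only the other 53 gives 41%, 66%, 93% and 99.6%. Each month of pause defers about 4 enrolments in a planned accrual of 60/4 = 15 months.

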10. ADVERSE EVENT REPORTING

Timely, accurate, and complete reporting and analysis of safety information is the responsibility of the PI and will be conducted in accordance with Institution policies.

The PRINCIPAL INVESTIGATOR will provide safety information to Janssen Scientific Affairs, LLC on adverse events, special situations including pregnancies and product quality complaints as defined below:

This Study has been designated as an interventional study. As such, all adverse events regardless of causality and special situations excluding those from subjects not exposed to a Janssen Medicinal Product and product quality complaints with or without an adverse event as described in this section will be reported from the time a subject has signed and dated an Informed Consent Form (ICF) until completion of the subject's last study-related procedure (which may include contact for follow-up safety). Serious adverse events will be reported for 30 days after the last dose of study drug.

For the purposes of this study, the Janssen medicinal product is: Ibrutinib (Imbruvica)

10.1 Adverse Event Definitions and Classifications

10.1.1 Adverse Events

An AE is any untoward medical occurrence in a patient or clinical investigation subject administered a medicinal (investigational or non-investigational) product and which does not necessarily have to have a causal relationship with this treatment. An AE can therefore be any unfavorable and unintended sign (including an abnormal laboratory finding), symptom, or disease temporally associated with the use of a medicinal (investigational or non-investigational) product, whether or not related to the medicinal (investigational or non-investigational) product. For the purposes of this study, AEs include events which are either new or represent detectable exacerbations of pre-existing conditions. The following are not considered an AE:

- Pre-existing condition: A pre-existing condition is not considered an AE unless the severity, frequency, or character of the event worsens during the study period.

Proprietary Information of MD Anderson

- Pre-planned or elective hospitalization: A hospitalization planned before signing the ICF is not considered an SAE, but rather a therapeutic intervention. However, if during the pre-planned hospitalization an event occurs which prolongs the hospitalization or meets any of the SAE criteria, the event will be considered an SAE. Hospitalizations for social reasons, solely for the administration of treatment, or due to long travel distances are not SAEs.
- Diagnostic testing and procedures: Testing and procedures should not be reported as AEs or SAEs but rather the cause for the test or procedure should be reported.
- Asymptomatic treatment related lymphocytosis: This event should not be considered an AE. Patients with treatment-related lymphocytosis should remain on treatment and continue with all study-related procedures.

10.1.2 Serious Adverse Event

An adverse event or suspected adverse reaction is considered “serious” if, in the view of either the investigator or the sponsor, it results in any of the following outcomes:

- Death
- A life-threatening adverse drug experience – any adverse experience that places the patient, in the view of the initial reporter, at immediate risk of death from the adverse experience as it occurred. It does not include an adverse experience that, had it occurred in a more severe form, might have caused death.
- Inpatient hospitalization or prolongation of existing hospitalization
- A persistent or significant incapacity or substantial disruption of the ability to conduct normal life functions.
- A congenital anomaly/birth defect.
- Is suspected transmission of any infectious agent via a medicinal product
- Is medically important
- Development of a secondary malignancy, excluding superficial, non-melanoma skin cancers or carcinoma in situ.

Medical and scientific judgment should be exercised in deciding whether expedited reporting is also appropriate in other situations, such as important medical events that may not result in death, be life-threatening, or require hospitalization may be considered a serious adverse drug experience when, based upon appropriate medical judgment, they may jeopardize the patient or subject and may require medical or surgical intervention to prevent one of the outcomes listed in this definition. Examples of such medical events include allergic bronchospasm requiring intensive treatment in an emergency room or at home, blood dyscrasias or convulsions that do not result in inpatient hospitalization, or the development of drug dependency or drug abuse (21 CFR 312.32).

- Important medical events as defined above, may also be considered serious adverse events. Any important medical event can and should be reported as an SAE if deemed appropriate by the Principal Investigator or the IND Sponsor, IND Office.
- All events occurring during the conduct of a protocol and meeting the definition of a SAE must be reported to the IRB in accordance with the timeframes and procedures outlined in “The University of Texas M. D. Anderson Cancer Center Institutional Review Board Policy for Investigators on Reporting Serious

Proprietary Information of MD Anderson

Unanticipated Adverse Events for Drugs and Devices". Unless stated otherwise in the protocol, all SAEs, expected or unexpected, must be reported to the IND Office, regardless of attribution (within 5 working days of knowledge of the event).

- **All life-threatening or fatal events**, that are unexpected, and related to the study drug, must have a written report submitted within **24 hours** (next working day) of knowledge of the event to the Safety Project Manager in the IND Office.
- Unless otherwise noted, the electronic SAE application (eSAE) will be utilized for safety reporting to the IND Office and MDACC IRB.
- Serious adverse events will be captured from the time a signed and dated ICF is obtained until 30 days following the last dose of study drug, unless the participant withdraws consent. Serious adverse events must be followed until clinical recovery is complete and laboratory tests have returned to baseline, progression of the event has stabilized, or there has been acceptable resolution of the event.
- Additionally, any serious adverse events that occur after the 30 day time period that are related to the study treatment must be reported to the IND Office. This will include the development of a secondary malignancy, except superficial, non-melanoma skin cancers or carcinoma in situ.

Reporting to FDA:

- Serious adverse events will be forwarded to FDA by the IND Sponsor (Safety Project Manager IND Office) according to 21 CFR 312.32.

It is the responsibility of the PI and the research team to ensure serious adverse events are reported according to the Code of Federal Regulations, Good Clinical Practices, the protocol guidelines, the sponsor's guidelines, and Institutional Review Board policy. Safety data includes adverse events, product quality complaints (PQCs), and special situations including pregnancies.

10.1.2.1 Pregnancy

Pregnancies and suspected pregnancies (including a positive pregnancy test regardless of age or disease state) of a female subject occurring while the subject is on study, or within 28 days of the subject's last dose of lenalidomide or ibrutinib, are considered immediately reportable events. Lenalidomide and/or ibrutinib are to be discontinued immediately. The pregnancy, suspected pregnancy, or positive pregnancy test must be reported to Janssen Scientific Affairs, LLC, using the Janssen Serious Adverse Event Form - and Celgene Drug Safety using the Pregnancy Initial Report Form, immediately by facsimile or email. The female subject should be referred to an obstetrician-gynecologist, preferably one experienced in reproductive toxicity for further evaluation and counseling.

The Investigator will follow the female subject until completion of the pregnancy, and must notify Janssen Scientific Affairs, LLC – using the Janssen Serious Adverse Event Form, and Celgene Drug Safety using the Pregnancy Follow-Up Report Form, immediately about the outcome of the pregnancy (either normal or abnormal outcome). If the outcome of the pregnancy was abnormal (e.g., spontaneous or therapeutic abortion), the Investigator should report the abnormal outcome as an AE. If the abnormal outcome meets any of the serious criteria, it must be reported as an SAE to Janssen Scientific Affairs, LLC

Proprietary Information of MD Anderson

and Celgene Drug Safety immediately by facsimile, or other appropriate method, within 24 hours of the Investigator's knowledge of the event using the SAE Report Form.

All neonatal deaths that occur within 28 days of birth should be reported, without regard to causality, as SAEs. In addition, any infant death after 28 days that the Investigator suspects is related to the in utero exposure to the investigational product should also be reported to Janssen Scientific Affairs, LLC using the Janssen Serious Adverse Event Form, and Celgene Drug Safety immediately by facsimile, or other appropriate method, within 24 hours of the Investigator's knowledge of the event. [Male Subjects](#)

If a female partner of a male subject taking investigational product becomes pregnant, the male subject taking lenalidomide should notify the Investigator, and the pregnant female partner should be advised to call their healthcare provider immediately.

The Principal Investigator is responsible for ensuring that these cases from clinical studies are complete and if not are promptly followed-up. This includes ensuring the reports are fully investigated and thoroughly documented by the Principal Investigator and that follow-up information is summarized e.g. hospital records, coroner's reports, autopsy results and recorded on the appropriate forms.

Because the effect of the Janssen medicinal product on sperm is unknown, pregnancies in partners of male subjects exposed to a Janssen medicinal product will be reported by the PRINCIPAL INVESTIGATOR within 24 hours of their knowledge of the event using the Serious Adverse Event Form. Depending on local legislation this may require prior consent of the partner.

Follow-up information regarding the outcome of the pregnancy and any postnatal sequelae in the infant will be required.

